- 10. Assess incidence of serious suicidal ideation and positive suicidal behavior assessed with the Columbia Suicide Severity Rating Scale (C-SSRS).
- 11. Assess mean changes in blood pressure, heart rate, and body temperature from pre-IP administration to end of each Experimental Session.

Recruitment and Participant Population

Therapy teams that have been identified to work on the sponsor's planned Phase 3 studies will treat at least one open-label participant in this study. Up to N=60 participants with a confirmed diagnosis of at least severe PTSD will be enrolled. Participants will be recruited through print and internet advertisements, referrals from other psychiatrists, psychotherapists, or physicians, and by

[figure not shown]
word of mouth. The sponsor will monitor demographics on an ongoing basis and encourage diversity in enrollment by communicating with sites.

Participants will be persons aged 18 or older, with a confirmed diagnosis of at least severe PTSD per the PCL-5 at Screening with symptoms present for at least 6 months. At Baseline, participants must qualify for a PTSD diagnosis per the CAPS-5 and have a Total Severity Score equal to or greater than 35 (severe). Participants would not be excluded for having more than one traumatic event or for having tried, not tolerated, or refused a selective serotonin reuptake inhibitor (SSRI) or serotonin norepinephrine reuptake inhibitor (SNRI) prescribed for PTSD. Participants with confirmed diagnosis of specific psychological and personality disorders will be excluded. Participants must be in good physical health and without major medical disorders that could affect the safety or tolerability of MDMA.

Statistical Analysis

All outcome analyses will be based on the *m*ITT analysis set. Change from Visit 3 (Baseline) in CAPS-5 Total Severity Scores to Visit 19 (Primary Outcome) will be analyzed with least squares means from a Mixed-Effect Repeated Measures model (MMRM). The *m*ITT analysis set will include all participants who receive IP in at least one Experimental Session and have at least one follow-up CAPS-5 assessment.

Study Structure Overview

MP16 Protocol IND #063384

Original Protocol Version 1: 18 May 2017 Amendment 1 Version 1: 03 January 2018

An Open-Label, Multi-Site Phase 2 Study of the Safety and Effect of Manualized MDMA-Assisted Psychotherapy for the Treatment of Severe Posttraumatic Stress Disorder

SPONSOR Multidisciplinary Association for Psychedelic Studies (MAPS)

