14.1.1 Effect Analyses

14.1.1.1 Primary Outcome Analyses

The primary analysis will be conducted after all participants complete Study Termination (Visit 20) and the study database has been locked. All outcome analyses will be based on the *m*ITT analysis set. The *de jure* estimand of treatment efficacy is of the most relevance to estimate the causal effect of three experimental sessions of MDMA-assisted psychotherapy in a controlled clinic setting on PTSD symptom severity in the intended population of patients with PTSD from any cause. The primary outcome measure, change from baseline in CAPS-5 score, will be analyzed with Mixed Model Repeated Measures (MMRM). The model will include terms for visit, baseline CAPS-5 score, and dissociative subtype (if possible). Ninety-five percent confidence intervals will be calculated for the estimated mean change from baseline CAPS-5 scores at each visit.

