## 7.0 Sample Size and Power Considerations

MP16 is a one-arm interventional study. Thus, no power nor sample size calculations were required.

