#### 8.0 Analyses

Every effort will be made to ensure complete, accurate and timely data collection and to avoid missing data, to ensure the completeness of the data which can impact the integrity and accuracy of the final study analysis. The statistical analyses will be reported using summary tables, figures, and data listings. All analyses and tabulations will be performed using SAS® Version 9.4 or higher, and S-PLUS. In general, nominal variables will be described in terms of frequencies and percentages. Ordinal and non-normal continuous variables will be described using sample median and range.

Approximately normal variables will be described using sample mean and standard deviations and analyzed by parametric statistical tests. Except for the primary effectiveness analysis, all statistical tests will be two-sided and a difference resulting in a p-value of less than or equal to 0.05 will be considered statistically significant. All p-values will be rounded to and displayed in four decimals. If a p-value less than 0.0001 occurs it will be shown in tables as <0.0001. Data not subject to analysis according to this plan will not appear in any tables or graphs, but will be included in the data listings. Selected results may be presented graphically using standard graphical software.

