#### 8.7.1 Primary Effectiveness Analyses

The *de jure* estimand of treatment effectiveness will be used to estimate the change in CAPS-5 score from baseline due to MDMA-assisted psychotherapy on PTSD symptom severity in the intended population of patients with PTSD from any cause. The primary estimator of effectiveness will be the mean change in CAPS-5 Total Severity Scores from Baseline to 18 weeks after start of dosing (Visit 19). Least squares means from a restricted maximum likelihood (REML)-based mixed model for repeated measures (MMRM) will be used to estimate the change in CAPS-5 from baseline to each visit. CAPS-5 data collected after treatment discontinuation will not be included in the *de jure* estimand. Missing data will not be imputed.

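### One-arm model with baseline CAPS-5 as covariate: the usual LS-mean 95% CI at Visit 19 leaves out the sampling error of the baseline mean and is too narrow if change depends on baseline

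*Protocol*

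**What the plan says.** Protocol 14.1.1.1 analyses change from baseline in CAPS-5 with an MMRM and lists its terms: "The model will include terms for visit, baseline CAPS-5 score, and dissociative subtype (if possible"). It then states that "Ninety-five percent confidence intervals will be calculated for the estimated mean change from baseline CAPS-5 scores at each visit". The effect is to be estimated "in the intended population of patients with PTSD from any cause". The Statistical Analysis paragraph of the protocol synopsis says that the Visit 19 estimate is a least squares mean.

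SAP 8.7.1 gives the same estimator: "Least squares means from a restricted maximum likelihood (REML)-based mixed model for repeated measures (MMRM) will be used to estimate the change". One such estimate is made for every CAPS-5 assessment after Visit 3. SAP 8.7.1 names no covariates. Neither document says at what baseline value the LS mean is evaluated, or how its variance is computed.

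The trial has one arm. SAP 7.0 draws the consequence: "Thus, no power nor sample size calculations were required". The documents therefore give no SD, correlation or expected interval width. Under Protocol 14.1.1.2 the SDS is analysed in the same way, so the point carries over to it.

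**The concern.** In a randomised comparison, adjusting for baseline sharpens the contrast, and the sampling error of the baseline mean cancels between arms. With one arm there is nothing to cancel it. The quantity of interest is the mean change itself, and if change depends on baseline, another sample with a different mean baseline would show a different mean change. The ordinary LS-mean SE treats the sample's mean baseline as a fixed number and leaves that variation out. The point estimate is essentially unaffected, but the interval is too short.

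With no control arm and no power calculation, the estimated change and its interval carry most of the inferential weight. The study is also meant to check assumptions behind the Phase 3 power calculations.

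**Working it through.** The plan gives no figure to reproduce, so the check is of the variance formula, with assumed inputs where the documents are silent.

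**Inputs from the documents**
- N up to 60 (Protocol 5.1) and up to 5% early termination (SAP 8.2), so n ≈ 60 × 0.95 = 57 at Visit 19.
- Baseline CAPS-5 at least 35 (Protocol 4.1, 8.2.2), which limits the baseline variance.

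**Assumed inputs (not in the documents)**
- Baseline SD sX: 5, 6 or 8.
- Visit 19 SD sY: 10, 13 or 15.
- Baseline-to-Visit 19 correlation ρ: 0, 0.2, 0.4 or 0.6.
- Complete data, with the subtype term left out.

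**Formulas**
- Slope of change on baseline: b = ρ·sY/sX − 1.
- Residual variance: s_res² = sY²(1 − ρ²).
- Usual LS-mean variance at the sample mean baseline: s_res²/n.
- Variance of the same estimate for the population mean change: (s_res² + b²·sX²)/n = (sX² + sY² − 2ρ·sX·sY)/n.
- SE ratio: √[s_res²/(s_res² + b²·sX²)] = √(1 − R²), where R² is the squared correlation of change with baseline.
- Approximate coverage: 2·T(t × ratio) − 1, where t is the 97.5% point on n − 2 df and T is the t distribution function on n − 1 df.

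**One case in full** (sX = 6, sY = 13, ρ = 0.2, n = 57)
- b = 0.2 × 13/6 − 1 = −0.567.
- s_res² = 169 × 0.96 = 162.24.
- Omitted term: 0.567² × 36 ≈ 11.56, so the total is 173.80.
- SE ratio = √(162.24/173.80) = 0.966.
- Half-width: 2.004 × √(162.24/57) = 3.38 as planned, and 2.003 × √(173.80/57) = 3.50 with the omitted term.
- Coverage of the planned interval: about 94.2%.

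**Other cases, n = 57**

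| sX | sY | ρ | b | SE ratio | Half-width, planned → full | Coverage |
|---|---|---|---|---|---|---|
| 6 | 13 | 0.4 | −0.13 | 0.998 | 3.16 → 3.17 | 95.0% |
| 6 | 13 | 0 | −1.00 | 0.908 | 3.45 → 3.80 | 92.6% |
| 8 | 13 | 0.2 | −0.68 | 0.921 | 3.38 → 3.67 | 93.0% |
| 6 | 10 | 0 | −1.00 | 0.857 | 2.65 → 3.09 | 90.9% |
| 8 | 10 | 0 | −1.00 | 0.781 | 2.65 → 3.40 | 87.7% |

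Of the 36 combinations (3 × 3 × 4), 28 have an SE ratio of 0.92 or more. In those 28, coverage is about 93–95% and the half-width shortfall is at most about 0.3 points. Four combinations fall below 91%, all with slopes of −0.75 or −1.0. The shortfall vanishes when ρ·sY/sX = 1, for example sX = 6, sY = 13 and ρ ≈ 0.46.

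**Simulation of the MMRM** (three visits, unstructured covariance, one common baseline slope, n = 57, 1,500 runs, baseline floored at 35). Monte Carlo error is about √(0.95 × 0.05/1500) = 0.6 percentage points.
- sX = 6: Visit 19 coverage was 94.4%, 94.8% and 93.9% at slopes 0, −0.3 and −0.6.
- sX = 8: coverage was 91.9% at slope −0.9.
- The plain SE of the raw change gave 94.4–95.7% in the same runs.
- When the true slopes differed by visit but one common slope was fitted, the first post-baseline visit had an SE ratio of 1.01 and 95.0% coverage.

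A larger simulation (20,000 runs, n = 57, baseline drawn from a truncated normal with mean 42 and SD 9) gave Visit 19 coverage of 94.1–94.7% at slope −0.4 and 90.8–92.7% at slope −0.8, against about 95% for the unadjusted change.

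**The case against.** Several arguments against the point have force.

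- **The slope is unknown.** If change is unrelated to baseline, nothing is lost, and the entry floor of 35 keeps the baseline variance down. This stands. It makes the point conditional, but the interval's validity should not rest on an unknown slope.
- **The method is unspecified.** The documents do not commit to evaluating the LS mean at the sample mean or to a model-based SE, and SAP 8.7.1 lists no baseline term although Protocol 14.0 makes the SAP the more detailed document. Run without that term, the model does not have the problem. This also stands. But the model written in Protocol 14.1.1.1, analysed with ordinary LS means, does have it.
- **Conditional inference is legitimate.** Regression intervals are commonly read as conditional on the observed covariates. The plan does not say that this is intended, and it names a population. Enrolled volunteers are not a random sample of that population, so the fuller variance does not settle generalisability. It only removes one known omission.
- **Little depends on it.** No success rule is tied to a confidence limit, and a few tenths of a point is small beside the 10 points that SAP 8.7.4 treats as clinically meaningful. This stands, and it limits the priority.

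A reader might infer that the interval is certainly too narrow, that every visit is affected, or that coverage near 91% is the expected result. The documents support none of these. They give no SD or slope, and with one common slope across visits an earlier visit need not be affected. The low coverage figures need steep slopes.

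SAP 8.0 also leaves the sidedness of any primary test open ("Except for the primary effectiveness analysis, all statistical tests will be two-sided"). That is a separate matter from the interval.

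**Conclusion.** The point holds in conditional form. With the protocol's model and a standard LS mean at the sample mean baseline, the Visit 19 interval for the population mean change is at best correct and otherwise too short. It is correct if the baseline slope is zero, or if the inference is declared conditional on the observed baselines.

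The likely size is small: an SE 0–8% too small in most of the assumed range. The worst assumed corner gives an SE about 22% too small. These figures rest on assumed SDs and correlations, n about 57 and complete data; the effect of missing data was not examined. This is a low-priority correction to the error bars, not a threat to the estimate.

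**What to change.** Fit the MMRM to the CAPS-5 scores themselves, with Visit 3 in the response vector alongside Visits 8, 13 and 19 and an unstructured covariance. Estimate Visit 19 minus Visit 3 with its 95% CI. This still uses baseline to inform missing follow-up, which dropping the covariate would not do. Equivalently, keep the present model and add b² × baseline variance / n to the variance of the LS mean. If conditional inference is intended, say so and state the baseline value used.

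Align Protocol 14.1.1.1 and SAP 8.7.1 on the model terms, and apply the same choice to the SDS.

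The cost is a changed model statement on the same data and a slightly wider interval, for example a half-width of 3.50 instead of 3.38 points in the case worked above.

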14.1.1.2 Secondary Outcome Analyses

Sheehan Disability Scale (SDS), the secondary outcome, will be analyzed in the same manner as the Primary Outcome.

14.1.1.3 Exploratory Analyses

One-group pretest-posttest Cohen's *d* effect size will be estimated. Exploratory sub-group analyses may be conducted when possible to evaluate effects and by individual demographic characteristics (e.g. age, gender, ethnicity, index trauma, dissociative subtype of PTSD, presence of secondary traumatic stressors during the assessment period with LEC-5, medication tapering, diagnosis of comorbid depression, diagnosis of comorbid Axis 2 diagnosis, and number of experimental sessions completed). Post-hoc exploratory analyses not described in the protocol or Statistical Analysis Plan may be performed to further examine the study data. These analyses will be clearly identified as such in the final clinical study report.

14.1.2 Safety Analyses

Safety data will be summarized by exposure to IP, unsolicited AEs, concomitant medications, suicidal ideation and behavior, and vital signs overall. If a participant has more than one AE mapped to the same PT, that AE will be reported once using the highest severity. AEs that occur on Day 0 (Experimental Session), Day 1, Day 2 after IP administration will be presented separately. Report incidence of AEs during Experimental Sessions such as clinical signs and symptoms, such as chest pain, shortness of breath, or neurological symptoms or any other signs or symptoms that may be indicative of a medical complication of the IP.

Frequency and incidence of concomitant medications will be displayed by generic name, sorted by class, and summarized by analysis set and category. Concomitant medications taken on Day 0 (Experimental Session), Day 1, Day 2 after IP administration will be presented separately. Any psychiatric concomitant medications will be tabulated by period (Preparatory, Treatment Period, Follow-up Period). Frequency and incidence of positive or serious ideation and suicidal behavior will be presented using descriptive statistics of C-SSRS scores in tabular format. Vital signs (heart rate, blood pressure, and body temperature) for Experimental Sessions will be summarized using descriptive statistics in tabular format listing values at pre-IP administration, prior to the supplemental dose, and at the end of each Experimental Session. Additional details are available in the Statistical Analysis Plan.

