3.3 Safety Objectives

The overall safety objective is to assess severity, incidence and frequency of AEs, AEs of Special Interest (AESIs), and Serious Adverse Events (SAEs), concomitant medication use, suicidal ideation and behavior, and vital signs to support the package insert for MDMA-assisted psychotherapy. The following safety objectives will evaluate the safety of MDMA-assisted psychotherapy.

- 1. Assess incidence of AEs during Experimental Sessions that may be indicative of a medical complication of the Investigational Product (IP), such as clinical signs and symptoms of chest pain, shortness of breath, or neurological symptoms or any other signs or symptoms that prompt additional vital sign measurements
- 2. Assess incidence of AEs by severity
- 3. Assess incidence of Treatment Emergent AEs (TEAEs) by severity
- 4. Assess incidence of TEAEs by severity taken during an Experimental Session and 2 days after IP administration
- 5. Assess incidence of AESIs, defined as AEs specified in the protocol related to cardiac function and abuse liability
- 6. Assess incidence of AEs by severity categorized as leading to discontinuation of IP, resulting in death or hospitalization, and continuing at Study Termination
- 7. Assess incidence of SAEs
- 8. Assess incidence of psychiatric concomitant medications taken during an Experimental Session and 2 days after IP administration
- 9. Assess incidence of any psychiatric concomitant medications taken during the Treatment Period

- MP16 Protocol Amendment 1 Version 1: 03 January 2018
- 10. Assess incidence of serious suicidal ideation and positive suicidal behavior assessed with the Columbia Suicide Severity Rating Scale (C-SSRS)
- 11. Assess mean changes in blood pressure, heart rate, and body temperature from pre-IP administration to end of each Experimental Session

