10.2.2.2 Psychological Risks and Mitigation

Mild anxiety and depressed mood are occasionally reported 1 to 3 days after MDMA administration [50, 114]. Psychological distress from MDMA could arise from the first indications of MDMA effects until the last effects have dissipated or even later. Anxiety or distress during the session may last for as little as 5 minutes or for as long as 5 hours or more. In addition, psychological distress could arise following an Experimental Session as a result of participants having difficulty integrating their experience after the MDMA effect has subsided. In previous Phase 1 and Phase 2 studies, these symptoms have been self-limiting and have responded well to reassurance from the therapy team, with occasional use of benzodiazepines for anxiety. In this study, participants will have the intention of confronting and working through traumatic experiences. Accordingly, signs of psychological distress, panic, or other unpleasant psychological reactions are to be expected and may be considered an element of the psychotherapeutic process.

MP16 Protocol

Proper preparation and follow-up support will reduce the difficulties participants might have with acute or sub-acute reactions. The potential for destabilizing psychological distress will be minimized by:

- Excluding people who might be more vulnerable to it (such as people diagnosed with bipolar affective disorder type 1 or with psychotic disorders)
- Preparatory Sessions of non-drug psychotherapy before the Experimental Session
- Creating an atmosphere of trust during the Experimental Session
- Close monitoring
- Phone contact with participants during the week after the Experimental Session
- **Integrative Sessions**
- Overnight stays at the study site for the night of each Experimental Session. Qualified personnel will be available during the overnight stay to respond to the needs of the participant. Attendants will be instructed to contact the therapy team upon request or at the appearance of signs of a potential Serious Adverse Event.

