10.2.4.1 Common AEs

Common AEs are typically observed during IP administration, but are transient and diminish as the IP is metabolized and excreted over the next 72 hours after dosing. Common AEs most frequently reported during Experimental Sessions include muscle tightness in the jaw, lack of appetite, dizziness, and nausea. During the week following treatment, lack of appetite, muscle tightness in the jaw, restlessness, weakness, dry mouth, thirst, impaired gait/balance, and sensitivity to cold may be reported. Severe anxiety, insomnia, fatigue, and depressed mood are commonly reported in PTSD studies in both placebo and MDMA groups. Common AEs are typically self-limiting. Elevations in anxiety and poor sleep respond to management with short-acting low dose benzodiazepines (specifically, lorazepam) or sleep aids as needed, per clinical judgment of the site physician.

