The sponsor and investigators agree that allowing participants who are screened for stable domestic circumstances to return home will not increase the risks of participation in the study. The study protocol discusses the risk of psychological distress in a PTSD population and mitigation in Section 10.2.2.2. Therapists and site physicians are aware of these risks, including anxiety and depressed mood occasionally reported 1 to 3 days after MDMA administration. In previous Phase 1 and 2 studies, these reactions have been transient and have responded well to reassurance from the therapy team, with occasional use of benzodiazepines for anxiety. If needed, the study physician may prescribe a short-acting, low-dose benzodiazepine (specifically, lorazepam) or sleep aids (excluding trazodone) as needed.

Consistent with the main study protocol and the sub-study, proper preparation and follow-up support will reduce the difficulties participants might have with acute or sub-acute reactions. The potential for destabilizing psychological distress will be minimized by:

- Excluding people who might be more vulnerable to it (such as people diagnosed with bipolar affective disorder type 1 or with psychotic disorders)
- Excluding people who do not have a stable living situation or supportive family/network
- Preparatory Sessions of non-drug psychotherapy before the Experimental Session
- Creating an atmosphere of trust during the Experimental Session

#063384 Amendment 1 Version 1: 03 January 2018

MP16 Protocol

- Close monitoring
- Phone contact with participants during the week after the Experimental Session
- Conduct of Integrative Session on the morning after the Experimental Session

Specific to sub-study:

- Therapist phone contact with participants on the night of the Experimental Session.
- A support person identified by the participant and agreed upon by the therapist must stay with the participant overnight on the evening following the Experimental Session.
- The therapists will meet with the support person prior to the first Experimental Session to
 assess their ability to act as an appropriate support person and to give them instructions
 about what to expect following Experimental Sessions and how to contact study
 personnel if needed.
- A support person must assist the participant during transfer from study site after the
 Experimental Session and to the study site on the following morning for the Integrative

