## 8.8.2 Analysis of Adverse Events

The primary measure of safety will be the reporting of unsolicited AEs. All AEs collected from Enrollment to Termination will be categorized as follows:

- Pretreatment AEs are defined as AEs that occur during the Preparatory Period prior to the first dose in the first Experimental Session
- Treatment Emergent AEs are defined as AEs that occur during the Treatment Period from the first Experimental Session to the last Integrative Session
- AEs that occur on and two days after MDMA or placebo administration
- AESIs are defined as AEs specified in the protocol related to cardiac function and abuse liability
- Follow-up Period AEs are defined as AEs that occur during the Follow-up Period after the last Integrative Session through Termination
- AEs leading to discontinuation of IP
- AEs resulting in death or hospitalization.
- SAEs
- AEs continuing at Termination.

Verbatim terms on case report forms will be mapped to preferred terms (PT) and system organ class (SOC) using the Medical Dictionary for Regulatory Activities (MedDRA) Version 17.0. Frequency and incidence of AEs will be displayed by PT, sorted by SOC, and summarized by treatment group, analysis set, category (as defined above), severity, and seriousness. AEs will be analyzed and presented as follows:

- If a participant has more than one AE mapped to the same PT, that AE will be reported once using the highest severity
- Relationship will be determined based on relative incidence of TEAEs with at least twofold difference between MDMA vs. placebo
- Compare relative incidence of AEs during Experimental Sessions such as clinical signs and symptoms, such as chest pain, shortness of breath, or neurological symptoms or any other signs or symptoms that may be indicative of a medical complication of the investigational product
- AEs that occur on day of Experimental Sessions and two days after IP administration will be presented separately.

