## 8.8.3 Concomitant Medications

A secondary measure of safety will be the reporting of concomitant medications. All concomitant medications collected from Screening to Study Termination will be categorized as follows:

- Pretreatment medications are defined as medications taken prior to and after signing informed consent and those taken during the Preparatory Period prior to the first Experimental Session. A stop date is expected prior to the first Experimental Session for any medications requiring a change in dose, a skipped dose, or tapering.
- Treatment Period concomitant medications are defined as those taken or continued during the Treatment Period from the first Experimental Session to the last Integrative Session. A stop date is expected prior to the each Experimental Session for any medications requiring a change in dose, a skipped dose, or tapering.
- Concomitant medications with a start date of the day of and two days after IP administration
- Follow-up Period concomitant medications are defined as those taken or continued during the Follow-up Period after the last Integrative Session through Termination
- Any concomitant medications that are tapered
- Any concomitant medications that are taken to treat an AE
- Any concomitant medications that are taken to treat an SAE
- Any excluded concomitant medications taken as a deviation from the protocol.

Concomitant medications on case report forms will be classified using the WHO Drug Dictionary EnhancedTM (WHO DDE). Frequency and incidence of concomitant medications will be displayed by generic name, sorted by class, and summarized by treatment group, analysis set, and category as defined above. Concomitant medications will be analyzed and presented as follows:

- Concomitant medications taken on the day of and two days after IP administration will be presented separately
- Any psychiatric concomitant medications by period.

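### The separate post-dose tables for AEs and medications end on Day 2, but the protocol places post-MDMA anxiety and low mood out to Day 3, so Day 3 onsets are left out of them

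*Protocol*

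**What the plan says.** The plan singles out the session day and the two days after it, and does so consistently.

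- **AEs.** Protocol 14.1.2: "AEs that occur on Day 0 (Experimental Session), Day 1, Day 2 after IP administration will be presented separately". SAP 8.8.2: "AEs that occur on day of Experimental Sessions and two days after IP administration will be presented separately". Objective 4 in Protocol 3.3 and its copy in SAP 3.3 set the same limit for treatment-emergent AEs by severity.
- **Medications.** Protocol 3.3, objective 8: "Assess incidence of psychiatric concomitant medications taken during an Experimental Session and 2 days after IP administration". Protocol 14.1.2: "Concomitant medications taken on Day 0 (Experimental Session), Day 1, Day 2 after IP administration will be presented separately". SAP 8.8.3 has a category for "Concomitant medications with a start date of the day of and two days after IP administration".

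The risk text describes a longer period for two psychiatric reactions. Protocol 10.2.2.2: "Mild anxiety and depressed mood are occasionally reported 1 to 3 days after MDMA administration". Appendix A repeats the timing: "anxiety and depressed mood occasionally reported 1 to 3 days after MDMA administration". Neither document says why the separate presentation stops at Day 2.

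**The concern.** The reporting window closes one day before the end of the period in which the protocol expects post-MDMA anxiety and low mood. A new episode on Day 3, or lorazepam or a sleep aid first given on Day 3, would not be counted with the dosing-linked events.

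Timing carries extra weight in this trial. Protocol 11.1 does not collect the investigator's view of relationship except for SAEs and leaves relationship to analysis. The rule in SAP 8.8.2 for that analysis is a twofold difference in incidence between MDMA and placebo. SAP 6.0 and 7.0 describe an open-label study with one arm, so the rule has no comparator and cannot be applied. Closeness to a dose is then one of the few planned means of separating non-serious reactions from background, and Protocol 3.3 says the safety results are to support the package insert.

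**Working it through.** No power, alpha or sample-size figure is involved. The check sets the window against the risk text and traces where a Day 3 event would be tabulated.

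1. **Day count.** Protocol 14.1.2 calls the session Day 0. One to three days after dosing is then Days 1, 2 and 3. The window covers Days 0, 1 and 2, so Day 3 is outside it.

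2. **What is missed.** An AE with onset on Days 0 to 2 is counted even if it lasts into Day 3. A drug started on Days 0 to 2 is counted even if it is continued. Only AEs with onset on Day 3 and drugs first started on Day 3 are missed. For drugs, Protocol 14.1.2 goes by use on those days while the SAP 8.8.3 category goes by start date; a first start on Day 3 fails both.

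3. **Where a Day 3 AE goes.** SAP 8.8.2 counts it as treatment-emergent, from the first Experimental Session to the last Integrative Session. That period is about 12 weeks (9 to 15 in Protocol 8.3). Repeat AEs with the same preferred term are reported once, at the highest severity, so a Day 3 anxiety event can merge with any other anxiety event of the period.

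4. **Where a Day 3 drug goes.** It enters the psychiatric medication table by period (Protocol 14.1.2, SAP 8.8.3) if it is psychiatric, and the SAP 8.8.3 category of drugs taken to treat an AE if given for one. Neither is indexed to a dose.

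5. **Whether the data exist.** Protocol 8.3.2 plans calls on Day 2 and Day 7 with two between, each asking about AEs and medications. Protocol 12.1 collects all medications through 7 days after the last session. Day 3 can be tabulated without new collection.

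6. **How much the window would grow.** Now: 3 days × 3 sessions = 9 days per participant. With Day 3: 4 × 3 = 12 days. The Treatment Period is about 12 × 7 = 84 days, so the share rises from 9/84 = 10.7% to 12/84 = 14.3%.

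7. **Possible size.** The documents give no rate of Day 3 onset. The most sessions the trial can hold is 60 × 3 = 180. As an assumption only, if 1%, 2% or 5% of sessions had a Day 3 onset, that would be 180 × 0.01 = 1.8, 180 × 0.02 = 3.6 or 180 × 0.05 = 9 sessions.

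**The case against.** The protocol and SAP agree with each other, and neither claims that this window captures every reaction to the drug. It is one cut among several: Protocol 14.1.2 and SAP 8.8.2 also plan a summary of AEs during sessions that may signal a medical complication, and SAP 8.8.2 has categories for AESIs, SAEs and AEs leading to discontinuation of IP. The reactions in question are called mild and occasional in Protocol 10.2.2.2, and the text does not say that any begin on Day 3. Extending by one day is also open to challenge, because Protocol 10.2.2.2 allows that distress may arise later still, and 10.2.4.1 lists reactions in the week after treatment. That section adds that severe anxiety, insomnia and depressed mood are common in both placebo and MDMA groups, so a wider window takes in more background.

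Much of this stands. There is no conflict between the two documents and no loss of data, and any cut-off is a judgement. What remains is that the plan stops short of the period its own risk text names for these reactions, without giving a reason. Coverage elsewhere does not tie the event to a dose, and the summary of AEs during sessions is narrower still.

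A reader might also infer support from Protocol 10.2.4.1, which says common AEs "are transient and diminish as the IP is metabolized and excreted over the next 72 hours after dosing". It does not give that support: the sentence describes how AEs decline, not when they start, and an AE that begins at the session is counted however long it lasts.

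**Conclusion.** The point holds as a mismatch between the reporting window and the protocol's own risk description. AEs with onset on Day 3 and medications first started on Day 3 are left out of the dosing-linked tables, although they remain in other planned tables. It rests on counting the session as Day 0, as Protocol 14.1.2 does, and on the 1-to-3-day statement in Protocol 10.2.2.2 and Appendix A.

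Two stronger readings are tempting. One is that a fixed share of these reactions is missed, one day in three. That would need onset to be spread evenly over the three days, and nothing in the documents supports it. The other is that acute psychiatric harm is understated. Without a Day 3 onset rate, the most that can be said is that dosing-linked psychiatric events may be understated. The 2 to 9 sessions in the working only show scale under an assumed rate. This is a cheap improvement, not a defect in the trial's safety monitoring.

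**What to change.** In Protocol 3.3 (objectives 4 and 8, and their copy in the synopsis), Protocol 14.1.2, and SAP 3.3, 8.8.2 and 8.8.3, extend the separate presentation of AEs and concomitant medications from Days 0 to 2 to Days 0 to 3. Keep the Day 0 to 2 row beside it, so that a reader can see what the added day contributes. Optionally add a Day 4 to 7 row, because Protocol 10.2.4.1 lists reactions in the following week.

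The cost is wording and one table parameter. No visit, call or form changes. The downside is that one more day per session, three per participant, falls inside the window, so a few more background events will be counted there; the retained Day 0 to 2 row shows how many events the extra day adds.
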